1.4 Models to be investigated

The following models will be validated:

- Risk of Malignancy Index (RMI) (Jacobs, 1990)
- IOTA LR2 model (Timmerman, 2005)
- IOTA Simple Rules (Timmerman 2008)
- IOTA Simple Rules Risk model (SRRisks) (Timmerman, 2016)
- IOTA ADNEX model (Van Calster, 2014)
- IOTA ADNEX without CA125 (Van Calster, 2014)

RMI, LR2, and SRRisks predict whether a tumor is malignant (vs benign), with borderline tumors being classified as malignant. ADNEX predicts malignant subgroups. More specifically, it gives 5 probabilities for each patient, for the following outcome categories: benign, borderline, stage I primary invasive, stage II-IV primary invasive, and secondary metastasis. One minus the probability of a benign tumor then equals the probability of malignancy.

In addition, we will also assess the performance of subjective assessment, which is customary in this field. We will assess subjective assessment as a binary judgment (benign vs malignant).

1.5 Statistical methods

1.5.1 Missing values for CA125 and outcome

CA125 was not mandatory in IOTA5, although it was highly encouraged. We expect missing values for CA125, for the following two reasons. First, following local protocols some centres were more committed than others to measure CA125. Second, the need to measure CA125 may depend on the overall clinical picture and the appearance of the tumour on ultrasound. Hence we expected clearly more missing values for cases that were followed up conservatively.

For some cases, as outlined above, the outcome is uncertain. The largest groups are cases without any information since the inclusion scan (U4 in the overview above), and cases with last FU <10 months after inclusion and without having had surgery and where the mass did not resolve spontaneously (U3).

Simply omitting cases with missing CA125 or outcome is likely to cause bias. For example, based on data from earlier IOTA studies, patients with missing CA125 have more often a benign tumor. The current data from IOTA5 indicate that CA125 is more often missing for patients that are followed conservatively than for patients that received surgery without follow-up visit. Further, we assume that conservatively followed patients with last follow-up <10 months will very often have a benign tumor.

Multiple imputation will be performed to deal with missing values for CA125 and outcome. Imputations will be created using the method of fully conditional specification with the mice package in R. We will generate 100 imputations, leading to 100 completed datasets. To estimate the missing values for CA125, we will use predictive mean matching regression using the outcome, variables that are probably related to either the level of CA125 itself, or to the unavailability of CA125 (i.e. a binary indicator indicating for each patient whether CA125 was missing). As the distribution of serum CA125 was heavily skewed, the log-log transformation of CA125 will be used (i.e., $\log(\log(\text{CA125} + 1))$). In the imputation model, the following variables will be used: Presumed endometrioma, level of certainty at subjective assessment at inclusion (6 groups: certainly benign, probably benign, benign but uncertain, malignant but uncertain, probably malignant, certainly malignant), patient age, type of center (oncological versus non-oncological center), lesion largest diameter, proportion of solid tissue (maximum diameter solid component divided by maximum diameter of lesion), number of locules (1, 2-10, >10, other), number of papillations, presence of shadows, presence of ascites, presence of metastases, bilaterality, pelvic pain, personal history of ovarian cancer, papillary height, papillary flow, color score, echogenicity of cyst fluid, and outcome (benign, borderline, stage I primary invasive, stage II-IV primary invasive, secondary metastatic). Descriptive characteristics of the tumor were based on the inclusion scan. Uncertain outcomes (cf above) will be considered missing, and hence the outcome will be imputed).

Note that some patients are classified as having a malignant tumor based on clinical and ultrasound information during follow-up (cf category M3 above). For these patients, we do not have a classification into one of the malignancy subtypes. The multiple imputation procedure will therefore treat the outcome as missing such that it will be imputed. The imputed outcomes will be evaluated, and the most commonly imputed malignant type will be used as the outcome in the analysis.

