All centres will receive the **IOTA 5 study screen**. At initial set up centres can choose between the two options:

- 1. Full IOTA 5 study (with planning of appropriate follow up and conservative management whenever feasible).
- 2. Observational study only (e.g. in radiology departments that are not involved in management decisions)

Recorded variables (entered in the astraia study screen).

Patient data

(click one option from list below)

- > New patient with diagnosis of adnexal mass
- ➢ New patient who was already in follow up in your centre for adnexal mass before she was enrolled to the IOTA 5 study. How many months in follow up? ...
- > Follow up scan of patient that is already enrolled to the IOTA 5 study before

Ultrasound

- Spontaneous resolution of the adnexal mass (no further details are entered)
- Adnexal mass present (fill in all variables below)
- 12 variables described in LR 1:
 - o Age
 - o personal history of ovarian cancer
 - o personal history of breast cancer
 - Max diameter of lesion
 - Max diameter of solid component
 - o Presence of ascites
 - o Presence of blood flow within papillary projection
 - o Irregular internal cyst walls
 - Presence of a purely solid tumour
 - Colour score (1/2/3/4)
 - Presence of acoustic shadows
 - Current hormonal therapy
 - Presence of pain during the examination
- as well as simple rules, RMI and other variables:
 - Type of tumour (unilocular/unilocular-solid/multilocular /multiloc-solid/solid)
 - Ovarian crescent sign
 - Cyst content
 - o Incomplete septum
 - o Mobility: mobile/reduced mobility/completely fixed
 - Number of locules
 - \circ Number of papillations (0/1/2/3/more)
 - Size of ovary
 - o Bilateral tumour
 - Evidence of metastases
 - Menopausal status: premenopausal/postmenopausal

- Serum CA 125 result (not mandatory)
- Symptoms during the last year before ultrasound scan (multiple options are possible)
 - Pelvic pain
 - Postmenopausal bleeding
 - o increased abdominal size
 - o persistent abdominal distention (bloating)
 - \circ appetite loss
 - \circ constipation
 - o diarrhoea
 - o urinary urgency
 - o urinary frequency
 - o weight changes
 - o dyspareunia
 - Other: please specify:
- For centres participating at the full IOTA 5 study only: Suggested management recorded by examiner: "What type of management do you propose for this patient based on ultrasound and clinical data?"
 - o Conservative management without follow up

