1.5.7. Subgroup analyses

We will compute the overall c-statistic for benign vs malignancy (i.e. after meta-analysis) and overall calibration curves for the following prespecified subgroups:

- By actual management: separate analysis of patients who were operated within 120 days after the first scan and without follow-up scan (similar to the population for the IOTA1-4 studies), and patients who received at least 1 follow-up scan; note that not all recruited patients fall within one of these two categories
- By suggested management ('intention to treat'): separate analysis of patients with suggested management surgery and patients with suggested management conservative
- By menopausal status: separate analysis of premenopausal patients and postmenopausal patient separately
- By type of center: separate analysis of patients examined in oncology centers and patients examined in other centers

The analysis of these subgroups will be done on data from the main centers, using meta-analysis if numbers allow. If numbers (e.g. number of patients with a malignancy) per center are too small, pooled analysis will be done.

No subgroup analyses are planned for the additional assessment of multinomial discrimination and calibration of the ADNEX model.

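### The imputation model for CA125 and outcome leaves out suggested management, although the SAP links conservative follow-up to missing CA125 and analyses subgroups by suggested management

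*SAP*

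**What the plan says.** The relevant text is section 1.5.1 of the SAP dated 28 May 2019.

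- **Rule for choosing predictors of CA125:** the outcome, plus "variables that are probably related to either the level of CA125 itself, or to the unavailability of CA125".
- **The list itself:** "In the imputation model, the following variables will be used: Presumed endometrioma, level of certainty at subjective assessment at inclusion", then age, type of centre (oncological or not), lesion and solid-tissue measurements, other scan features, pelvic pain, history of ovarian cancer and the five-category outcome. That makes 19 items. None records suggested management, surgery or follow-up, and the tumour descriptors come from the inclusion scan.
- **Reasons given for missing CA125:** "First, following local protocols some centres were more committed than others to measure CA125", and "Second, the need to measure CA125 may depend on the overall clinical picture and the appearance of the tumour on ultrasound". More missing values under conservative follow-up are presented as a consequence of these two reasons. The SAP then confirms the pattern from the data: "The current data from IOTA5 indicate that CA125 is more often missing for patients that are followed conservatively than for patients that received surgery".
- **Missing outcome:** "we assume that conservatively followed patients with last follow-up <10 months will very often have a benign tumor".

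Section 1.5.7 prespecifies a "separate analysis of patients with suggested management surgery and patients with suggested management conservative". The protocol's list of recorded variables shows that full-study centres enter the answer to this question at the scan: "What type of management do you propose for this patient based on ultrasound and clinical data"? Section 1.5.2 says that RMI and ADNEX with CA125 are evaluated on imputed CA125 in every analysis.

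**The concern.** The list does not follow the SAP's own rule. A recorded baseline variable, closely tied to a factor that the SAP associates with missing CA125, is left out. An imputation model that ignores management treats a woman sent to follow-up and a woman sent to surgery as exchangeable when their listed variables agree. The missing values of the first are then partly borrowed from the second.

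This matters in two places. The objective (section 1.1 of that SAP) is performance in all women, including those followed conservatively, and that is where CA125 is most often missing. In addition, the subgroups by suggested management would be analysed on data imputed as if the grouping carried no information. An error in imputed CA125 enters RMI and ADNEX with CA125 directly, but not LR2 or ADNEX without CA125, so it could also disturb that comparison.

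**Working it through.** The documents give no missingness rates and no bias figure, so there is nothing to reproduce. All rates below are assumptions.

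**1. When omission biases imputed malignancy.** Take women who share the listed variables. Let w be the operated share of those with known outcome, and p_op and p_cons the malignancy risks. Without management in the model, the imputed risk is w·p_op + (1 − w)·p_cons, so

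bias in conservatively managed women = w·(p_op − p_cons).

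Example: p_cons = 1% and a residual odds ratio of 3 give p_op = 0.03/1.02 = 2.94%. At w = 0.3 the bias is 0.3 × 1.94 = +0.58 points.

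| p_cons = 1%, residual OR | w = 0.1 | w = 0.3 | w = 0.5 |
|---|---|---|---|
| 0.67 | −0.03 | −0.10 | −0.16 |
| 1 | 0 | 0 | 0 |
| 1.5 | +0.05 | +0.15 | +0.25 |
| 3 | +0.19 | +0.58 | +0.97 |

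The sign is that of the residual association.

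**2. CA125 and outcome imputed together.** Simulation with 200,000 women and one completed dataset per setting. It used chained equations, with predictive mean matching on log(log(CA125 + 1)) and logistic imputation of a binary outcome. Assumed: CA125 observed in 75% of operated and 35% of conservative women; outcome missing in 2% and 25%. Results are for conservative women with the value missing, as truth / management omitted / management included.

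| Residual log OR; CA125 shift | Malignancy, % | Median CA125 |
|---|---|---|
| 0; 0 | 3.3 / 3.3 / 3.5 | 15.7 / 15.5 / 15.6 |
| 0.7; 0.05 | 2.5 / 3.5 / 2.6 | 15.6 / 16.5 / 15.5 |
| 1.4; 0.10 | 1.9 / 3.9 / 1.9 | 15.5 / 17.6 / 15.4 |
| −0.7; −0.05 | 4.4 / 3.4 / 4.5 | 15.8 / 14.6 / 15.7 |

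The first row shows that differences of about 0.2 points are within simulation noise. In these settings, including management recovers the truth whichever way the link runs.

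**3. Effect on accuracy.** A second simulation used 60,000 women, with CA125 missing in 60% of conservative and 20% of operated women and outcome missing in 30% of conservative women. Log-odds of surgery, per unit ln CA125 and per SD of other clinical information, were 0.3, 0.6 and 1.0. With management omitted, specificity of a CA125-based score in conservative women was 92.7%, 92.7% and 92.8%, against true values of 93.3%, 94.2% and 95.0%. Sensitivity was 81%, 78% and 76%, against 77%, 74% and 68%. Overall specificity was 0.3 to 1.3 points too low. This simulation lets CA125 influence surgery whether or not it was measured.

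**4. Subgroup contrast.** Let f_c and f_s be the missing shares of CA125 in the conservative and surgery groups, and w now the surgery share of women with observed CA125. With listed variables equal, the part of a true difference in mean transformed CA125 that survives imputation is

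1 − f_c·w − f_s·(1 − w).

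Using step 2's assumed rates (f_c = 0.65, f_s = 0.25) and equal group sizes, w = 0.75/(0.75 + 0.35) = 0.682. The surviving part is 1 − 0.443 − 0.080 = 48%. If 20% of the women go to surgery, w = 0.15/0.43 = 0.349 and 61% survives. If 80% do, w = 0.60/0.67 = 0.896 and 39% survives. If there is no residual difference, nothing is lost.

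**5. Would a planned analysis reveal it?** Excluding the uncertain-outcome groups U1 to U4 (section 1.5.8) partly probes the outcome side. It leaves CA125 imputation in place (section 1.5.2). No listed analysis varies the CA125 imputation model.

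**The case against.** The SAP's two stated reasons are centre practice and the clinical and ultrasound picture, and the list covers the second well through six-level certainty, about a dozen scan features and pelvic pain. The protocol ties eligibility for conservative management to the examiner's certainty that the mass is benign, and certainty is in the model. Some recorded reasons for surgery, such as fertility concerns or patient request, do not signal malignancy. Conservatively managed women also supply many known outcomes themselves. The residual link could therefore be small. This stands as an argument about size. It does not explain why a recorded variable that meets the SAP's rule and defines a subgroup is absent.

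The fix can also do harm. An unmeasured CA125 cannot have influenced the decision. In a simulation where measurement preceded management and only measured values affected surgery (log-odds 0.3, 0.6, 1.0), mean ln CA125 in unmeasured conservative women was truly 2.67 throughout. Omitting management gave 2.67, 2.66 and 2.67. Adding it gave 2.60, 2.53 and 2.48. This stands, and is why both models should be reported.

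For outcome, a term for actual management would be unsound. Its no-information level would be group U4, where every outcome is missing, so its coefficient cannot be estimated. Malignancies operated on after 120 days become missing (U1) unless every assessment was malignant, and M3 is also set to missing, so followed women lose malignancies selectively. With a residual log OR of 0.7 and half of conservative malignancies removed, true prevalence was 4.1%, against 3.3% with management omitted and 2.2% with it added. Suggested management is known at inclusion for U4 women too at full-study centres, so it avoids the first problem. It shares the second to the extent that suggestion and actual course coincide.

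**Conclusion.** The omission is plain from the text and is a moderate, cheaply repaired flaw. Its consequence is conditional: bias arises only if management is related to CA125 or malignancy after the listed variables are taken into account. Under the assumed links, imputed malignancy in the affected women was off by about 1 to 2 percentage points and median CA125 by about 1 to 2 units. With no link there was no bias.

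Two stronger readings are tempting. A reader might infer that the SAP names management as the driver of missing CA125. It does not: it names centre practice and the clinical and ultrasound picture, and presents management as a resulting pattern. A reader might also infer that CA125 and malignancy are imputed too high in conservatively followed women. Upward bias is plausible, because raised CA125 is a recorded reason for surgery and clinicians select lower-risk masses for follow-up. The documents contain nothing that settles the sign or size.

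One assumption remains. The SAP's statement about missing CA125 concerns the course actually followed, and suggested management is taken here as a close baseline counterpart.

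**What to change.** Add suggested management at inclusion (conservative versus surgery) to the imputation model for CA125 and for outcome, and to the section 1.5.8 analysis that re-imputes outcomes derived from subjective assessment. Report the currently listed model as a sensitivity analysis, and say in the text that the two models bracket different assumptions about whether measured CA125 influenced the suggestion.

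Do not add an actual-management term with a no-information level to the outcome model. Menopausal status need not be added either: age is already listed, and the follow-up SAP of 27 December 2017 (section 1.2.2) reports a software fault that overwrites the baseline value with that of the last visit.

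The cost is one SAP sentence, one extra parameter and one extra imputation run. The variable is recorded at full-study centres only, and the documents do not say which centres, if any, were observational only. Where it was not recorded, it would have to be imputed as well, or the listed model kept for that analysis.

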1.5.3 Discrimination between benign and malignant tumors

We will calculate the c-statistic (i.e. AUC) per center, and calculate an overall AUC using random effects meta-analysis on the logit of the center-specific AUCs. In case multiple imputed data are used (e.g. models that include CA125, or when multiply imputed outcome are used), the $\text{logit}(AUC)$ is calculated for each center and herein for each imputed dataset. The latter estimates will then be combined using Rubin's rules and the resulting estimates will be used in a random-effects model to get a final estimate of the AUC.

Sensitivity and specificity will be calculated at the following cut-offs (for models that give predicted risks): 1%, 3%, 5%, 10%, 15%, 20%, 25%, 30%, 40%, and 50%. For the non-imputed data, a bivariate random-effects model will be used to calculate an overall result that takes the clustering by center into account. For imputed data, center-specific sensitivity and specificity as well as their variance (i.e. standard error squared) will be computed, and combined using Rubin's Rules to obtain a final center-specific estimate. These will be used in a bivariate random-effects model to come to a final estimate.

For RMI, we will use cut-offs of 25, 100, 200, and 250. For the Simple Rules classification, we will combine the inconclusive cases with the cases classified as malignant, i.e. inconclusive cases will be classified as malignant.

Because risk models and RMI are on a different scale, it is difficult to directly compare sensitivity or specificity. Therefore, we also calculate the sensitivity when fixing the specificity at 90%, and the specificity when fixing the sensitivity at 90%.

For subjective assessment, we will quantify the overall sensitivity and specificity using a bivariate random-effects model.

For Simple Rules, we will report the percentage of inconclusive cases, and specificity and sensitivity when inconclusives are classified as malignant. This will be done using meta-analysis techniques.

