1.5.4. Calibration of the risk of malignancy

For non-imputed data, a random-effects logistic model will be used to compute both the calibration intercept and slope. The overall calibration curve will be computed using the results of the latter for an average center. The average center corresponds to a center where the calibration intercept and slope equal the fixed effect estimates (i.e. the random components are 0). Center-specific calibration curves will be computed using the empirical Bayes-estimates. For imputed data, the calibration intercept and slope will be computed per center and herein per imputed dataset by use of a logistic regression model.

Hereafter, the estimates will be combined using Rubin's Rules to get center-specific estimates and these estimates will be used in a random-effects model to get an overall estimate. For the overall calibration curve as well as for the center-specific calibration curves, this will be computed for each imputed dataset using the same method as for the non-imputed data and the results of the imputed datasets will be combined using Rubin's Rules.

The RMI does not give predicted risks. Therefore, similar to the IOTA3 validation study (Testa 2014), we will construct calibration curves conditional on the RMI score.

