1.5.5. Clinical utility

We will calculate Net Benefit (NB) for risk thresholds between 5% and 50%, for using models to decide which patients to refer for specialized oncological care (Wynants 2017). For each center and threshold, we will make an average 2x2 cross-tabulation over the 100 imputed datasets. The cross-tabulation contrasts outcome (benign vs malignant) vs classification (risk<threshold vs risk≥threshold). This is used to calculate NB. Using meta-analysis, the center-specific NBs at a given threshold are combined into an overall estimate (Wynants, 2018).

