1.5.6. Additional analysis for ADNEX

We will further analyse the ADNEX predictions in terms of discrimination and calibration. First, c-statistics between each pair of outcome categories will be computed using the conditional method (Van Calster, 2012). Only pooled results will be shown (i.e. no meta-analysis) because some outcome categories will have few events in several centers. For imputed data, logit(AUC) will be computed for each imputation, and combined using Rubin Rules.

Second, multinomial logistic calibration curves will be constructed (Van Hoorde 2014). For imputed data, curves will be derived per imputed dataset, and averaged.

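### The imputation model contains centre type but not individual centre, although imputed data are analysed per centre; if centres differ, their spread and the pooled calibration interval are understated

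*SAP*

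**What the plan says.** All references are to the SAP section dated 28 May 2019 unless stated.

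- **Imputation model (1.5.1).** CA125 and uncertain outcomes are imputed by fully conditional specification, 100 times. The variable list includes "patient age, type of center (oncological versus non-oncological center), lesion largest diameter, proportion of solid tissue". No centre factor, centre random effect or multilevel imputation method is mentioned.
- **Selection rule (1.5.1).** For CA125 the plan says it will use "variables that are probably related to either the level of CA125 itself, or to the unavailability of CA125". The first reason it gives for missing CA125 is that "following local protocols some centres were more committed than others to measure CA125".
- **Discrimination (1.5.3).** "We will calculate the c-statistic (i.e. AUC) per center, and calculate an overall AUC using random effects meta-analysis". Sensitivity and specificity are also obtained per centre, combined by Rubin's rules and then pooled.
- **Calibration (1.5.4).** For imputed data, "the calibration intercept and slope will be computed per center and herein per imputed dataset", followed by Rubin's rules and a random-effects model. For centre curves, "Center-specific calibration curves will be computed using the empirical Bayes-estimates"; the same method is applied within each imputed dataset.
- **Clinical utility (1.5.5).** "Using meta-analysis, the center-specific NBs at a given threshold are combined into an overall estimate".
- **Status (1.5.2).** The analysis of imputed CA125 and outcome is primary.

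**The concern.** The analysis model lets each centre have its own performance. The imputation model assumes that, given type and the patient-level covariates, all centres are alike. Each imputed outcome therefore carries the average relation between covariates and malignancy, not that of the patient's own centre. If centres do differ, the completed data understate the difference in proportion to how much of the information was imputed.

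Two planned outputs depend on that difference: the between-centre variance, which sets the width of the pooled random-effects interval, and the centre-specific calibration curves. The curves would look more alike than they should, beyond the shrinkage that empirical Bayes intends.

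Individual centre also meets the SAP's own rule for choosing CA125 imputation variables, because the plan itself links missing CA125 to centre practice.

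No planned analysis would show the effect. The analysis without uncertain outcomes (1.5.8) reports overall c-statistics and overall calibration curves, not centre curves, and models with CA125 still use imputed values there (1.5.2). The other sensitivity analysis imputes more outcomes, again with no centre term stated.

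**Working it through.** **1. Inputs.** From the documents: 17 main centres (SAP 1.3 and 1.5.8); at least 3,000 women planned (protocol, Number of study patients). Not given: missing fraction, malignancy rate, and residual variation between centres. There is no plan figure to reproduce, so the size must be simulated under stated assumptions.

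**2. Mechanism.** Let u_j be the true calibration intercept of centre j and f the share of calibration information, Σp(1−p), that is imputed. Without centre in the imputation model, the completed-data intercept is roughly (1−f)·u_j. A simulation with 17 centres, 4,000 patients and centre SD 0.5 gave:

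| Missing outcomes | f | 1−f | Simulated slope of centre estimates on truth |
|---|---|---|---|
| 10 / 20 / 40%, unrelated to risk | 0.10 / 0.20 / 0.40 | 0.90 / 0.80 / 0.60 | 0.91 / 0.81 / 0.62 |
| 10 / 20 / 40%, mostly low-risk masses | 0.04 / 0.09 / 0.24 | 0.96 / 0.91 / 0.76 | 0.97 / 0.92 / 0.77 |

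The rule fits. It also shows why the malignancy rate among imputed patients matters: p(1−p) is 0.12 × 0.88 = 0.106 at a risk of 12%, but 0.05 × 0.95 = 0.048 at 5%.

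**3. From spread to interval width.** Approximately, SE² = τ²/17 + within-centre part. With complete data the 95% width is 0.507, so SE = 0.507/3.92 = 0.129. With estimated τ = 0.49, τ²/17 = 0.0141, which leaves 0.0167 − 0.0141 = 0.0026 for the within-centre part. At 20% missing, unrelated to risk and with centre type only, estimated τ falls to 0.38. Then SE = √(0.38²/17 + 0.0026) = √(0.0085 + 0.0026) = 0.105 and width = 0.413. The simulated width was 0.427, that is 0.427/0.507 = 0.84 of complete data.

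**4. Main simulation.** Assumptions:
- 17 centres and 5,100 patients, about 20% malignant.
- Outcome logit = linear predictor (mean −2.4, SD 2.0) + 0.3 for oncology type + centre effect (SD 0.3 or 0.5).
- Missingness depends on the linear predictor with slope b.
- Imputation by logistic regression on linear predictor and type, with or without a centre random intercept.
- Analysis by calibration intercept per centre (slope fixed at 1), Rubin's rules and DerSimonian-Laird pooling.

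Ratios to complete data at 10 / 20 / 30% missing, over repeated runs:

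| Quantity | Type only, b = −0.3 (imputed patients 11-13% malignant) | Type only, b = −0.8 (4-6% malignant) | With centre, b = −0.3 |
|---|---|---|---|
| Pooled SE | 0.95-0.96 / 0.89-0.92 / 0.82-0.87 | 0.98 / 0.94-0.96 / 0.89-0.92 | 0.98-1.00 |
| Between-centre SD | 0.93-0.94 / 0.84-0.86 / 0.74-0.78 | 0.97 / 0.92-0.93 / 0.86 | 0.98-0.99 / 0.95-0.98 / 0.91-0.96 |

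At b = −0.3, coverage of the nominal 95% interval was 0.91-0.93 / 0.88-0.91 / 0.83-0.87 without centre and 0.92-0.93 / 0.92 / 0.91 with it, against 0.93 with complete data. At b = −0.8 it fell by about 1 to 3 points. The spread of empirical-Bayes centre intercepts at b = −0.3 was 0.93 / 0.84-0.85 / 0.76 without centre and 0.98-1.00 with it.

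**5. Limits of the effect.**
- 5% missing (b = −0.3, centre SD 0.5): SE ratio 0.98, empirical-Bayes spread 0.96.
- b = −1.2, 10% missing (imputed patients 2% malignant): SE ratio 0.99.
- Centres identical beyond type: SE ratio 0.95-0.98 without centre and 0.99 with it.
- Pooled intercept: shift of at most 0.02. With missingness correlated −0.5 or +0.5 with the centre effect (30% missing, SD 0.5), the shift was +0.05 or −0.02 without centre and +0.02 or −0.01 with it.

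**The case against.** The strongest reply has four parts.

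**The condition is not shown.** Nothing in the documents says that centres differ in malignancy once six-level certainty, ascites, metastases, solid proportion, colour score and oncology type are taken into account. This stands; the SD of 0.3 to 0.5 is an assumption.

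**The imputed patients are probably mostly benign.** SAP 1.5.1 assumes this for conservatively followed patients with last follow-up under 10 months, one of the two largest uncertain groups. The main centres were also chosen for good follow-up and surgery data (1.3), which makes high missing fractions less likely. Both arguments stand. They roughly halve the effect at a given missing fraction and make the 30% case a poor anchor. The risk in the other large group, patients with no information after inclusion, is not stated.

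**Parsimony is defensible.** SAP 1.5.6 expects that "some outcome categories will have few events in several centers", so sixteen centre indicators in a five-category outcome model could fail. This argues against that particular form of the model, not against a penalised or random intercept for benign versus malignant.

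**A check is already planned.** For models without CA125, 1.5.8 gives overall calibration free of imputation. That is true, but it does not report centre curves, and omitting uncertain cases brings the selection bias that 1.5.1 warns about.

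A reader might go further and infer that uneven CA125 measurement biases the imputed CA125 values. The documents describe who is measured, not CA125 levels given the covariates, so this does not follow. Nor does the uneven follow-up adherence noted in the 2017 plan show that malignancy differs between centres. In the simulation, centre variation in missingness alone changed the ratios by at most 0.01.

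**Conclusion.** The mismatch is real and worth correcting, but its consequence is conditional and modest. If centres differ beyond type and covariates, the between-centre variance is understated, the pooled calibration-intercept interval is too narrow by roughly 2 to 5% at 10% missing and 5 to 10% at 20% missing, and centre calibration curves are drawn together. The lower figures apply if imputed patients are mostly benign, which is closer to the SAP's own expectation for short follow-up. At 5% missing, or with almost entirely benign imputed patients, the loss is 1 to 2%.

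A reader might infer that the overall performance estimates are biased. The calculations do not support that: the pooled intercept hardly moves. A reader might also carry these percentages over to AUC, calibration slope, sensitivity and specificity, net benefit or CA125 imputation. None of these was quantified, so for them only the mismatch itself is established.

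**What to change.** In SAP 1.5.1, add individual centre to the imputation model:

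- as a 17-level factor in the predictive mean matching model for CA125;
- as a random or penalised intercept for benign versus malignant, with the malignant subtype imputed without centre where categories are sparse.

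If this does not converge, keep the present model and run the centre version as a sensitivity analysis. Include centre in the separate all-centre imputation (1.5.8) for CA125. Report, by centre, the fraction of missing outcomes and the imputed beside the observed malignancy rates, so that readers can see how far imputation drives each centre's result.

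Cost: no new data, and statistician time only. The imputation becomes more complex and may converge poorly in sparse centres. If centres do not differ, centre estimates gain slight noise (empirical-Bayes spread 1.04-1.17 of complete data, against 0.98-1.00 without centre). A centre intercept would not fully restore centre differences in slope or AUC.
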